6.5.1.2 Dose Modification, Interruption, and Discontinuation of Xevinapant Treatment

For participants who do not tolerate the study intervention, adjustments to the study intervention dose are permitted to allow the participant to continue on-study intervention according to the guidelines below.

The guidelines for xevinapant dose modifications for toxicities considered at least possibly related to study intervention are outlined in Table 7 and Table 8, for combination therapy and monotherapy, respectively. These dose modifications are recommendations unless otherwise specified as mandatory. All dose modifications should be based on the worst preceding toxicity (NCI-CTCAE v5.0). Additionally, nontreatment-related events, or unexpected toxicities may require interruption of study intervention at the discretion of the Investigator.

In case a dose reduction is necessary, the study intervention will be administered as follows:
For each participant, a maximum of 2 dose reductions of xevinapant will be allowed during the study.

The volume of the oral solution equivalent to each dose level is the following:

- Planned dose (Level 0): CCI corresponds to CCI mg/day of xevinapant
- Dose Level 1: CCI corresponds to CCI mg/day of xevinapant
- Dose Level 2: CCI corresponds to CCI mg/day of xevinapant

General rules for xevinapant administration throughout the treatment period (C1 to C6) are:

[figure not shown]
- The number of treatment days with xevinapant intake should not exceed 14 days per cycle.
- In case of tolerability issues, up to 2 sequential xevinapant dose reductions of CCI mg/day (CCI of oral solution) per step will be allowed, down to a minimum dose of CCI mg

CCI [REDACTED] of oral solution). If further dose reduction is required, the participant must be permanently discontinued from xevinapant administration (other ongoing treatments can continue, see Sections 6.5.2 and 6.5.3).

[figure not shown]
- If the onset of several toxicities leads to conflicting recommendations as described in Table 7 the most conservative dose adjustment among all toxicities presented must be followed.
- **No re-escalation** of xevinapant dose after dose reduction will be allowed during the study. Once xevinapant dose has been reduced, participant will keep receiving the same dose until the EOT, or until further dose reduction or permanent treatment discontinuation, if required due to tolerability issues.
- Xevinapant doses that were omitted on a specific day should **NOT** under any circumstances be administered any other day in addition to the scheduled intake.
- No additional dose should be re-administered after vomiting; the participant must wait for the next scheduled intake.
- Combination treatment period: If IMRT is interrupted, xevinapant should be interrupted. If IMRT is restarted, xevinapant should be resumed at the next originally scheduled intake day of xevinapant, provided other rules of dose interruption are not met (see Section 6.5.3.3). If IMRT is permanently discontinued due to safety issues, then xevinapant administration should be maintained, and the participant can enter the monotherapy period. Otherwise, xevinapant treatment should be discontinued permanently, the EOT visit should be performed, and the participant should stay on study for follow-up as per protocol. IMRT may be interrupted for up to a maximum of 10 treatment days in total.
- Monotherapy treatment period: If a participant requires a xevinapant dose interruption of more than 21 consecutive days due to study intervention-related toxicities, the Investigator should consider discontinuing the treatment. If a participant is discontinued from the monotherapy treatment, the EOT visit should be performed. Hereafter, the participant will continue with the study as per schedule and will enter the FU period.
- Chemotherapy discontinuation will **NOT** result in xevinapant discontinuation.
- Participants who prematurely discontinue from all treatments, i.e. chemotherapy, IMRT, and xevinapant, in the absence of disease progression will undergo the EOT visit and then enter the follow-up period according to schedule.
- Any dose modification and dose interruption including the reason must be recorded on the Dosage Administration Record eCRF.

CCI

CCI

CCI

CCI

CCI

[figure not shown]
CCI

CCI

CCI

CCI

CCI

[figure not shown]

CCI

CCI

CCI

6.5.1.3 End of Xevinapant Treatment

Xevinapant treatment will be administered until the 6 cycles of therapy (i.e. 3 cycles of combination therapy followed by 3 cycles of monotherapy) are completed or until any of the study intervention discontinuation criteria described in Section 7.1 occur.

Note: If IMRT is permanently discontinued due to severe or intolerable toxicities as per Investigator's discretion, then the participant can enter the monotherapy period.

Discontinuation from study intervention does not mean discontinuation from the study. Procedures to be followed in the event of a study intervention discontinuation are presented in Section 7.1.

Procedures for discontinuation from study (not only study intervention) are described in Section 7.2.

6.5.2 Chemotherapy

All participants will receive cisplatin (CCI) mg/m²) intravenously over at least 90 minutes on Day 2 QW up to a maximum of 7 cycles in total (see administration schedule in Table 2). If body surface area is > 2.00 m², the maximum dose per infusion will be capped at a maximum of 80 mg.

A total cumulative cisplatin dose of CCI mg/m² is recommended (Machiels 2020), based on various studies suggesting a sufficient therapeutic effect when this exposure to cisplatin is met (Strojan 2015, Szturz 2019). Please consult and follow cisplatin administration instructions provided in your local label and institutional guidelines. The infusion has to be administered with pre- and postinfusion hydration ± mannitol and/or diuretics. Any pre-existing dehydration should be corrected. Please refer to Appendix 3 and Appendix 4 for additional information on cisplatin administration and hydration regimen respectively.

CCI

eGFR (using the CKD-EPI creatinine formula) should be ≥ 60 mL/min/1.73 m² before administration of cisplatin at C1D2; retreatment conditions as specified in Table 7 should be met.

Participants should receive at least 1 full cisplatin infusion, such as on C1D2, before dose reduction, or switch to carboplatin.

Standard antiemetic prophylaxis for cisplatin containing regimens is mandatory starting on Day 1 of each chemotherapy containing cycle. Standard antiemetics guidelines (administration of pre- and post-treatment serotonin receptor antagonists, neurokinin-1 receptor antagonists and dexamethasone [or any other corticosteroid at equivalent dose iv] according to the 2016 MASCC and ESMO guideline (Roila 2016) are provided in Section 6.8.1.1; however, the specifics of the regimen are at the discretion of the treating physician, provided adequate control is achieved.

Note: Please refer to Section 6.8.1.1 for the proposed adjusted dosage/schedule for dexamethasone and aprepitant due to perpetrator drug-drug interaction potential of xevinapant via inhibition of CYP3A4.

A participant not eligible to continue with QW cisplatin after dose reduction can switch to carboplatin as per the dose modifications outlined in [Table 7](#) (NCCN Chemotherapy Order Templates 2020). Please consult and follow the carboplatin administration instructions provided in your local label.

No pre- or post-treatment hydration or forced diuresis is required for carboplatin administration.

6.5.2.1 Dose Modification, Interruption, and Discontinuation of Chemotherapy

Permitted cisplatin dose levels:

- Planned dose (level 0): corresponds to cisplatin **CCI** mg/m²
- Dose level - 1: corresponds to cisplatin **CCI** mg/m² **CCI**
- Dose level - 2: corresponds to cisplatin **CCI** mg/m² **CCI**

For participants switching to carboplatin: carboplatin AUC = 2 mg·min/mL is allowed.

Please refer to [Table 7](#) for instructions on dose modifications, interruption, discontinuation of chemotherapy, and potential switch to carboplatin in case of toxicity suspected to be related to study intervention.

Toxicity related to chemotherapy administration includes but is not limited to nausea, vomiting, renal toxicity (with an elevation of blood urea nitrogen and creatinine and impairment of endogenous creatinine clearance, as well as renal tubular damage, which appears to be transient), peripheral neuropathy, ototoxicity (with hearing loss that initially is in the high-frequency range, as well as tinnitus), and hyperuricemia. Much more severe and prolonged toxicity has been observed in participants with abnormal or obstructed urinary excretory tracts. Myelosuppression, often with delayed anemia, is expected.

Chemotherapy dose adjustments at the start of a cycle should be based on the nadir of hematologic counts or maximum nonhematologic toxicity from the previous treatment cycle. Chemotherapy infusion may be delayed to allow for sufficient recovery time.

6.5.2.2 End of Chemotherapy

Chemotherapy will be administered until completion of the 7 weekly infusions of platinum-based therapy planned in the study or until any of the study intervention discontinuation criteria described in Section 7.1 occur.

Note: Chemotherapy discontinuation will **not** automatically have to result in xevinapant discontinuation or IMRT discontinuation

Dose modifications, treatment interruption, switching from cisplatin to carboplatin, and permanent discontinuation of any of the components of the study intervention is to be recorded in the Dosing CRF of each component of the study intervention. For each action, the reason must be recorded.

Discontinuation from study intervention does not mean discontinuation from the study. Procedures to be followed in the event of a study intervention discontinuation are presented in Section 7.1.

Procedures for discontinuation from study (not only study intervention) are described in Section 7.2.

6.5.3 Radiotherapy

6.5.3.1 General Considerations

The general recommendation is to start IMRT as soon as a diagnosis and management decision has been decided.

The following guidelines must be applied:

- **Nutritional support:** Maintaining adequate nutrition is essential during the course of radiotherapy (Section 6.8.4.1).
- **Dental care:** Before the participants start IMRT, dental assessment is mandatory, and appropriate dental care should be provided (Section 6.8.4.2).

Refer to the RT Manual for further guidance.

6.5.3.2 Treatment

Full details of radiotherapy protocol requirements including volumes, OAR, and OAR dose constraints can be found in the RT Manual provided for this study. A QA procedure will be applied for this study. The RT-QA Review Center (Appendix 5) will centrally review the IMRT treatment plan(s) including other treatment-related information submitted by the Investigator to ensure compliance with protocol guidelines and provide feedback to the site (refer to the RT Manual). The IMRT plan must be reviewed by the RT-QA Review Center prior to the start of the IMRT. A summary of radiotherapy requirements and recommendations is described below.

CCI

A matched conventional anterior neck field is not permitted. During treatment, daily image-guided radiation therapy (IGRT) is required with either kV or MV guidance.

For CT simulation, the participant must be in a supine position and immobilized with a thermoplastic (or similar) mask that includes the head and neck with strong consideration of the shoulders as well. Intraoral immobilization devices are at the discretion of the Investigator. A slice thickness of 3 mm or less is required and the field of view must extend from the top of skull to the bottom of the carina. Intravenous contrast is recommended at the time of simulation.

Standard fractionation IMRT (as fully described in the IMRT manual) is to be started on C1D1 after administration of xevinapant (see administration schedule in [Table 2](#)). On days where all treatment components should be administered, IMRT should be preferably administered after xevinapant and chemotherapy.

IMRT will be delivered per [Table 9](#) and the following:

- To the PTV and high-risk clinical target volume: 70 Gy in 35 fractions over 7 weeks, 2.0 Gy/fraction, 5 days/week. Missed treatments due to holidays or logistic reasons can be compensated by delivering the missed fraction before or after the end of the combination treatment period (i.e. up to Week 9 after administration of first dose) (see Section [6.5.3.3](#)).
- Elective irradiation (low risk) to locoregional areas, 56 Gy (1.6 Gy/fraction per day, 5 fractions per week [5/7 days]).

Table 9 **Radiation Therapy Scheme**

	Total dose in Gy	Dose in Gy	Number of days	
PTV 70	70	2	35	5 fractions per week over 7 weeks
PTV 56	56	1.6	35	5 fractions per week over 7 weeks

PTV=Planning target volume.

The delineation of the elective nodal clinical target volume for participants with positive neck nodes can be based on the consensus guidelines published by Biau ([Biau 2019](#)). Additional details will be provided in the RT Manual.

PTV will be a uniform 3 to 5 mm expansion to all clinical target volumes to account for interfraction motion and setup uncertainties. The simultaneous integrated boost treatment plan will be prescribed to the PTV and coverage requirements are detailed in the Radiotherapy Guidelines. If a PTV is close to the spinal cord or other critical normal tissue, a PTVeal can be created and adjusted for treatment planning purposes. The requirements for organ at risk definition and dose constraints are listed in the RT Manual.

All participants will have daily pretreatment imaging to ensure appropriate repositioning, the details will be described in the RT Manual.

The RT-QA Review Center ([Appendix 5](#)) will centrally review the IMRT treatment plan(s) to ensure compliance with protocol guidelines and provide feedback to the site.

The IMRT treatment plan for each participant must be submitted electronically to the RT-QA Review Center as soon as possible and no later than 5 business days prior to the start of IMRT. The digital data must include treatment planning of CT scan, structure, plan, and dose files (please refer to the RT Manual). The RT-QA Review Center will evaluate IMRT delivery and any critical/major deviations from the submitted plan during study intervention period. RT-QA Review Center review of the IMRT plan is requested before starting the first fraction administration.

6.5.3.3 Treatment Interruption

IMRT interruption is strongly discouraged, and every attempt should be made to keep the treatment continuous and adhere to the overall treatment time as prescribed (7 weeks). Planned radiotherapy interruptions are not allowed. Any interruption must be clearly indicated in the treatment record and reasons should be documented.

IMRT may be interrupted for up to a maximum of 10 treatment days in total to allow resolution/improvement of radio-chemo toxicities such as Grade 4 mucositis measured by physical or functional examination, or Grade 4 radiodermatitis (see Section [6.5.3.4](#) for management of those toxicities).

Treatment interruption due to a nonmedical reason should be minimized as much as possible and should not exceed 2 consecutive treatment days per interruption ([Radiologists 2019](#)). In case of interruption for technical reasons (e.g. malfunction or revision of the treatment machine), continued treatment must be ensured, and the use of another unit is recommended. For units that have different energy levels, it is recommended to perform the dosimetry on an alternative device.

If a fraction has to be compensated, it can be administered after the planned 35 fractionation days (Cycle 1 to 3) or it can be compensated during the 35 fractionation days. If compensated during the 35 fractionation days, the fractions should be at least 6 hours apart. Xevinapant administration should not be compensated. In any case, there must be no more than 5 days of treatment in a given week.

If IMRT is permanently discontinued due to severe and intolerable toxicities as per Investigator's judgment, then xevinapant monotherapy administration should be maintained, and the participant can enter the monotherapy period.

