Participant diary dispensation	X																							See Section 8.6
Weekly cisplatin		X			X			X			X			X			X		X		X		See Section 6.5.2	
IMRT			5 fractions/week for 7 weeks																				See Section 6.5.3	
Other clinical Assessments																								
Concomitant therapy	X	X	X	X	X	X	X	X	X	X	X	X	X	X	X	X	X	X	X	X	X			
Adverse events	X	X	X	X	X	X	X	X	X	X	X	X	X	X	X	X	X	X	X	X	X	Including SAE and AESI		
Ancillary Studies																								
Xevinapant blood PK			X			X					X												See details in Table 4	
CCI																								

AESI = adverse events of special interest, CxD1 = Cycle x Day 1, ECG = electrocardiogram, ECOG PS = Eastern Cooperative Oncology Group Performance Status, CT = Computed Tomography, IMRT = Intensity-modulated radiation therapy, MRI = Magnetic Resonance Imaging, PK = pharmacokinetic, SAE = serious adverse event.

[figure not shown]
Table 3 Schedule of Activities: Monotherapy Period (Cycle 4 till Cycle 6) and Follow-up Period

Study period	Monotherapy period (Xevinapant)			EOT	FU/E OS	Notes
Cycle	Cycle 4	Cycle 5	Cycle 6			
Cycle Day	1	1	1			
Study Week	10	13	16	20	3QM	
Study Day	64	85	106	134		
Visit Window (days)	±3 d	±3 d	±3 d	±7 d	±2 w/ ±1 m	EOT 14 d (± 7 d) after last study intervention administration (xevinapant, cisplatin), or IMRT whichever is last or 14 d (± 7 d) after premature treatment discontinuation but prior to start of new anticancer therapy. In case of premature treatment discontinuation imaging and clinical tumor assessments must be performed according to original schedule (Week 20 for EOT assessment)" FU at least 3 QM until last on-study participant reaches their 18-month post-first treatment visit (EOS), a decision to end study has been triggered, or until premature discontinuation from study, whichever occurs first. At this point, all remaining participants will have an EOS visit (±1 m) unless last FU visit was done < 6 weeks before.
Physical exam	X	X	X	X	X	Complete examination at EOT; until PD
ECOG PS	X	X	X	X	X	Until PD
Vital Signs	X	X	X	X		Including weight
Nutritional status	X			X		See Section 6.8.4.1
Dental examination (See Appendix 9)				X		
Audiometry	(X)			Only if clinically indicated. See Section 8.2.7		
Laboratory assessments						
Blood hematology	X	X	X	X		Local laboratory
Blood biochemistry – full panel	X	X	X	X		Local laboratory
Coagulation				X		Local laboratory
Pregnancy test	X	X	X	X	X	In FU every 4 weeks up to 9 months after first treatment
Urinalysis	X			X		Local laboratory

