6.5.3.4 Management of Acute "in Radiation Field" Toxicity

If dermatitis, mucositis, or dysphagia occurs, the possibility of IMRT interruption should be assessed according to their severity. Institutional guidelines on prophylaxis and dental hygiene will be followed for management of skin and mucosal toxicity.

For any other degree of minor toxicity, the necessary support measures must be taken to ensure treatment continuity ([Peterson 2015](#)).

In the event of mucositis, the following recommendations will be considered:

- Rapid escalation of analgesics using the World Health Organization cancer pain relief ladder ([WHO 2018](#)).
- Enteral or parenteral nutritional support according to the institutional guideline. Enteral nutritional support is strongly recommended if weight loss is $\geq 5\%$. If the weight loss is $\geq 10\%$, the use of a nasogastric or gastrostomy tube must be implemented as quickly as possible ([Elad 2019](#)) and access to adequate nutritional support needs to be secured by the Investigator.

The management of radiation dermatitis should be based on the severity of symptoms, as determined by Radiation Therapy Oncology Group and should follow the recommendations by the Supportive Care Guidelines Group.

6.5.3.5 **End of Radiotherapy**

Radiotherapy will be administered until completion of the IMRT dose and schedule (see [Table 9](#)) planned in the study or until any of the study intervention discontinuation criteria described in Section [7.1](#) occur.

Note: Radiotherapy discontinuation will not result in xevinapant discontinuation or chemotherapy discontinuation. See further Section [6.5.1.3](#).

Treatment interruption and permanent discontinuation of any of the components of the study intervention is to be recorded in the Dosing CRF of each component of the study intervention. For each action, the reason must be recorded.

Discontinuation from study intervention does not mean discontinuation from the study. Procedures to be followed in the event of a study intervention discontinuation are presented in Section [7.1](#).

Procedures for discontinuation from study (not only study intervention) are described in Section [7.2](#).

6.6 **Continued Access to Study Intervention After the End of the Study**

Not applicable

6.7 **Treatment of Overdose**

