7.1 Discontinuation of Study Intervention

Study intervention (i.e. xevinapant, cisplatin, and IMRT) must be discontinued under the following circumstances:

- Disease progression, including clinical progression as judged by the Investigator, treatment failure, local, or distant relapse, second cancers, or start of any new anticancer treatment including salvage surgery.
- Participant withdrawal of consent for treatment.
- Participants may voluntarily discontinue one or several of the study interventions at any time. If such discontinuation occurs, every effort should be made by the Investigator to determine the primary/underlying reason for this decision, which should be recorded in the eCRF. The participant should be encouraged to remain on study to be followed for efficacy assessments.
- Unacceptable toxicity/AEs that result in a significant risk to the participant's safety.
- Participants who are removed from study intervention due to AEs must be treated and followed up for these AEs according to standard medical practices.
- Any protocol deviation that results in a significant risk to the participant's safety, only after discussion with Sponsor.
- Noncompliance that is deemed by the Investigator or the Sponsor to compromise participant safety or study integrity.
- Pregnancy (Section [8.3.4](#)).
- Investigator decision in the participant's best interest. The primary reason for this decision (e.g. lack of efficacy, AE) must be recorded in the eCRF.
- Early study termination by the Sponsor, SMC, the Investigator, the IEC/IRB, or the Regulatory Agencies.

The primary reason for study intervention discontinuation must be recorded in the eCRF.

If study intervention is permanently discontinued, the participant will remain in the study to be evaluated for safety and efficacy. The SoA indicates data to be collected at the time of discontinuation of study intervention and follow-up and for any further evaluations that need to be completed (

Table 3- EOT visit).

7.1.3 **Temporary Discontinuation**

See Section 6.5.1.2 (xevinapant), Section 6.5.2.1 (cisplatin), and Section 6.5.3.3 (RT) for further guidance on temporary discontinuation of treatment.

7.1.4 **Rechallenge**

See Section 6.5.1.2 for details on study intervention restart or rechallenge criteria.

7.1.4.1 **Study Intervention Restart or Rechallenge After Liver Stopping Criteria Are Met**

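### After a permanent IMRT stop, the readable protocol sections disagree on whether xevinapant and cisplatin continue; this affects treatment and exposure more than the primary endpoint.

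*Protocol*

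**What the plan says.** **Toxicity or safety reasons.**

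- Protocol 6.5.1.2: "If IMRT is permanently discontinued due to safety issues, then xevinapant administration should be maintained, and the participant can enter the monotherapy period".
- Protocol 6.5.1.3, for severe or intolerable toxicity: "then the participant can enter the monotherapy period".
- Protocol 6.5.3.3, for severe and intolerable toxicity: "then xevinapant monotherapy administration should be maintained, and the participant can enter the monotherapy period".

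None of these passages mentions cisplatin or carboplatin. Table 3 schedules the monotherapy period (Cycles 4 to 6, from Day 64) with xevinapant as its only treatment.

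**Any reason.** The note in Protocol 6.5.3.5 reads: "Radiotherapy discontinuation will not result in xevinapant discontinuation or chemotherapy discontinuation". It then refers to 6.5.1.3. Protocol 6.5.2.2 ends chemotherapy at seven weekly infusions or when a Section 7.1 criterion occurs. It does not list an IMRT stop as a reason.

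**General discontinuation rule.** Protocol 7.1: "Study intervention (i.e. xevinapant, cisplatin, and IMRT) must be discontinued under the following circumstances". One item on its list is "Unacceptable toxicity/AEs that result in a significant risk to the participant's safety". Section 6.5.3.5 names the 7.1 criteria as what ends radiotherapy before completion.

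**Non-safety reasons.** After the safety case, Protocol 6.5.1.2 continues: "Otherwise, xevinapant treatment should be discontinued permanently, the EOT visit should be performed".

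**The concern.** A permanent IMRT stop is foreseeable in this population. A site looking up what to do next finds different answers in different sections. Read as written, the toxicity case supports three courses: xevinapant alone, xevinapant with the remaining chemotherapy, or nothing further. The start of monotherapy is also open, since the text does not say whether it begins at once or at the scheduled Cycle 4. In the non-safety case, two sections give opposite instructions on xevinapant.

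At stake is consistent treatment of participants who have just had a serious toxicity, and the interpretability of the exposure and safety data from a small single-arm study. The primary endpoint also uses dose-based rules, so it has to be checked whether the conflict reaches it.

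**Working it through.** The plan states no figure on this point, so the check compares the passages and then works out the exposure.

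**1. The passages side by side, after a permanent IMRT stop**

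| Section | Reason for stop | Xevinapant | Chemotherapy |
|---|---|---|---|
| 6.5.1.2 | safety | continues; may enter monotherapy | not mentioned |
| 6.5.1.2 | otherwise | stops permanently | not mentioned |
| 6.5.1.3 | toxicity | may enter monotherapy | not mentioned |
| 6.5.3.3 | toxicity | monotherapy continues | not mentioned |
| 6.5.3.5 | any | not stopped | not stopped |
| 6.5.2.2 | IMRT stop not listed | no rule given | continues to 7 infusions or a 7.1 criterion |
| 7.1 | unacceptable toxicity, significant risk | stops | stops |

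On xevinapant after a non-safety stop, the second and fifth rows contradict each other without any inference. On chemotherapy after a toxicity stop, the conflict arises in two ways: if monotherapy is taken to start at once, or if the 7.1 criterion is met. The rule in 6.5.1.2 to follow the most conservative adjustment covers only several toxicities that give conflicting Table 7 advice. It does not rank these sections.

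**2. Cisplatin exposure**

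Inputs: Table 2 places infusions on Days 2, 9, 16, 23, 30, 37 and 44, which is 7 in all. The DLT-like assessment period is 5 weeks (Days 1 to 35) and contains 5 of them. Cycle 1 contains 3 and Cycle 2 contains 3. Full doses are assumed until the stop.

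| If cisplatin ends with IMRT on | Whole course | 5-week window | Cycle 1 | Cycle 2 |
|---|---|---|---|---|
| Days 10–15 | 2/7 = 29% | 2/5 = 40% | 2/3 = 67% | 0/3 |
| Days 17–22 | 3/7 = 43% | 3/5 = 60% | 3/3 | 0/3 |
| Days 24–29 | 4/7 = 57% | 4/5 = 80% | 3/3 | 1/3 = 33% |
| Chemotherapy continues | up to 7/7 | up to 5/5 | up to 3/3 | up to 3/3 |

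**3. Xevinapant exposure, non-safety stop**

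Planned dosing days are 6 cycles × 14 = 84. If IMRT stops on Day 15, 6.5.1.2 gives 14/84 = 17% of planned days, while 6.5.3.5 allows up to 84/84.

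**4. Does it reach the primary endpoint?**

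- The 40% figure (2/5) belongs to the two rules that use the 5-week window: at least 60% received for the DLT analysis set (Table 16), and more than 40% missed for the intercurrent event (Protocol Section 3).
- The dose criterion in 8.2.5.1 is per treatment cycle. For a stop on Days 10–15, the Cycle 1 value is 67%, above 60%. A stop on Days 17–22 meets the window rules at exactly 60% but gives 0/3 in Cycle 2, if those infusions remain in the planned dose.
- The intercurrent event is limited to reasons other than a treatment-related AE. Toxicity that ends IMRT would normally be treatment-related, so it falls outside.
- Under 8.2.5.1, Grade 3 or higher nonhematologic toxicity generally counts as a DLT-like event. The common Grade 3 CRT toxicities that are otherwise excepted count if they lead to permanent discontinuation of treatment.
- A confirmed DLT-like event puts the participant in the DLT analysis set whatever dose was given, so the 60% rule does not decide inclusion.

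**The case against.** The strongest reply is that the toxicity sections can be read consistently. Sections 6.5.1.2 and 6.5.1.3 concern xevinapant and answer only whether it may go on. Chemotherapy follows its own rule in 6.5.2.2, which agrees with 6.5.3.5. If monotherapy begins at its scheduled Day 64, the last cisplatin infusion on Day 44 is already past and nothing conflicts. Section 7.1 is a general list that does not name an IMRT stop. The same list lets a participant give up one or several components, and other sections treat single-component stops as ordinary. Tables 7 and 8 are redacted and may settle the matter.

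Much of this stands. A reader might infer that 6.5.1.3 says the opposite of 6.5.3.5. It does not: it is silent on cisplatin, and its wording is permissive. A reader might also infer that 7.1 withdraws all three components after every toxicity-driven IMRT stop. Its text conflicts only when the toxicity is also unacceptable with significant risk. It cannot be said that the plan contains no governing rule, only that none is readable.

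The reply leaves two things unanswered. The consistent reading has to be supplied by the reader, and it fits 6.5.3.3 poorly, since that section speaks of maintaining monotherapy at the point where IMRT ends. Nor does it touch the non-safety case, where 6.5.1.2 and 6.5.3.5 cannot both be followed. A rule in the redacted tables would not remove the disagreement between the readable sections.

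**Conclusion.** The concern holds as an internal inconsistency in treatment instructions. It is firm for xevinapant after a non-safety IMRT stop. It is a real ambiguity for chemotherapy after a toxicity stop. Its size is in exposure: for a stop on Days 10 to 15, 2 of 7 against up to 7 of 7 cisplatin infusions, assuming full doses and the two extreme readings.

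A reader might go further and infer that a participant passes or fails the primary endpoint according to the section followed. The documents do not support that as a general statement. Most such participants are already DLT-like events through the toxicity and enter the DLT set regardless of dose. The intercurrent event excludes treatment-related AEs, and the 40% figure is not the per-cycle measure in 8.2.5.1. This rests on the toxicity being judged treatment-related and confirmed by the SMC. One residual uncertainty is whether permanent discontinuation of treatment in the 8.2.5.1 exception means one component or all three, the same question as in 7.1.

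Practical weight is reduced further by SAP Section 7.1, which limits reporting to a first SMC analysis with 6 patients and a synoptic CSR whose list contains no DLT-like rate table. Cumulative dose, dose intensity and therapy delays are still listed, so the exposure question remains.

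**What to change.** Reconcile Protocol 6.5.1.2, 6.5.1.3, 6.5.2.2, 6.5.3.3, 6.5.3.5 and 7.1. One place should state, separately for toxicity and for other reasons, what happens to xevinapant and to cisplatin or carboplatin after a permanent IMRT stop, and when the monotherapy period begins. The other sections should refer to it. Section 7.1 should say whether its requirement applies to the affected component or to all three. The choice of clinical rule is the sponsor's, and none is proposed here.

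The cost is wording in one amendment, with no added data. If an amendment is no longer worthwhile given the reduced scope, the synoptic CSR can state which rule was applied to each participant whose IMRT was permanently stopped.
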